11 ADVERSE EXPERIENCE REPORTING AND DOCUMENTATION

11.1 Adverse Events

Definition of an AE: Any untoward medical occurrence in a subject administered a pharmaceutical product that does not necessarily have a causal relationship with the treatment. An AE can therefore be any unfavorable and unintended sign (including an abnormal laboratory finding), symptom, or disease temporally associated with the use of a medicinal (investigational) product, whether or not considered related to the investigational medicinal product.

Investigational Medicinal Product (IMP) includes the drug under evaluation and the comparator drug(s) if specified as part of the research objective, given at any time during the study. Medical conditions/diseases present before starting the drug of interest are only considered adverse events if they worsen after starting the drug of interest.

The occurrence of adverse events will be sought by non-directive questioning of the patient at each visit during the study. Adverse events also may be detected when they are volunteered by the patient during or between visits or through physical examination, laboratory test, or other assessments. All adverse events will be recorded in the study database including the following information:

1. the severity grade (mild, moderate, severe)
2. its relationship to the drug(s) of interest (suspected/not suspected)
3. its duration (start and end dates or if continuing at final exam)
4. whether it constitutes a serious adverse event (SAE)

AE Severity

The National Cancer Institute's Common Terminology Criteria for Adverse Events (CTCAE) Version 3.0 should be used to assess and grade AE severity, including laboratory abnormalities judged to be clinically significant. The modified criteria can be found in the study manual. If the experience is not covered in the modified criteria, the guidelines shown in **Error! Reference source not found.** below should be used to grade severity. It should be pointed out that the term "severe" is a measure of intensity and that a severe AE is not necessarily serious.

Table 1. AE Severity Grading

Severity (Toxicity Grade)	Description
Mild (1)	Transient or mild discomfort; no limitation in activity; no medical intervention or therapy required. The subject may be aware of the sign or symptom but tolerates it reasonably well.
Moderate (2)	Mild to moderate limitation in activity, no or minimal medical intervention/therapy required.

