Severe (3)	Marked limitation in activity, medical intervention/therapy required, hospitalizations possible.
Life-threatening (4)	The subject is at risk of death due to the adverse experience as it occurred. This does not refer to an experience that hypothetically might have caused death if it were more severe.

Table 2. AE Relationship to Study Drug

Relationship to Drug	Comment
Definitely	Previously known toxicity of agent; or an event that follows a reasonable temporal sequence from administration of the drug; that follows a known or expected response pattern to the suspected drug; that is confirmed by stopping or reducing the dosage of the drug; and that is not explained by any other reasonable hypothesis.
Probably	An event that follows a reasonable temporal sequence from administration of the drug; that follows a known or expected response pattern to the suspected drug; that is confirmed by stopping or reducing the dosage of the drug; and that is unlikely to be explained by the known characteristics of the subject's clinical state or by other interventions.
Possibly	An event that follows a reasonable temporal sequence from administration of the drug; that follows a known or expected response pattern to that suspected drug; but that could readily have been produced by a number of other factors.

Unrelated	An event that can be determined with certainty to have no relationship to the study drug.
-----------	---

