11.2 Serious Adverse Experiences (SAE)

A SAE is any untoward medical occurrence that at any dose:

- results in death,
- is life-threatening,
- requires inpatient hospitalization or prolongation of existing hospitalization,
- results in persistent or significant disability/incapacity,
- is a congenital anomaly/birth defect,
- is otherwise a significant medical event.

This includes any SAEs likely to arise from the trial indication or progression of underlying/concomitant illness(es) (e.g. progression of cancer in oncology trials), unless specified in the protocol as study specific exemptions.

Any SAE, irrespective of causality, occurring after the subject has provided informed consent and until four weeks after the subject has stopped study participation must be reported unless otherwise stated in the protocol. SAEs occurring after four weeks from ending study participation should only be reported if considered by the Investigator attributable to the exposure to the investigational drug(s) during the trial period. This includes the period in which the study protocol interferes with the standard medical treatment given to a subject, even if study treatment has not yet started (e.g. withdrawal of previous treatment during washout period, change in treatment to a fixed dose of concomitant medication).

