14.2 Analysis of Secondary Endpoints

1. Efficacy Endpoints

- a.** EASI and IGA scores at week 16 will be compared to baseline.

2. Safety Endpoints

- a.** Safety will be evaluated by tabulation of adverse events (AEs), including any Serious Adverse Events (SAEs) within treatment groups. All AEs occurring during the study will be recorded. Descriptions of adverse events will include the date of onset, the date the adverse event ended, the severity of the adverse event, and the outcome. All reported adverse events will be summarized by the number of subjects reporting adverse events, body system, severity, seriousness, and relationship to study treatment.

3. Analysis of Other Endpoints

- a.** Other variables may be analyzed and presented descriptively. The methods to be used will include (but are not limited to) parametric and nonparametric analysis, means, standard deviations, frequency counts and graphs, as appropriate.
- b.** Video footage of patient experiences will be compiled at the end of the study. The compiled video footage will subsequently be watched and analyzed to further understand the experiences of atopic dermatitis patients, and how undergoing dupilumab treatment alters these patients' experiences and attitudes with their skin disease.

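### The causality scale in section 11.1, Table 2 has no class for an unexpected reaction, and the plan does not say which relatedness scale will be tabulated

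*Combined protocol and SAP*

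**What the plan says.** Table 2 in section 11.1 defines four classes.

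- **Definitely** has two routes. It opens with "Previously known toxicity of agent; or an event that follows a reasonable temporal sequence from administration of the drug", and the second route goes on to require an event "that follows a known or expected response pattern to the suspected drug; that is confirmed by stopping or reducing the dosage of the drug", with no other reasonable explanation.
- **Probably** asks for the same timing, pattern and confirmation on stopping or reducing, with other explanations unlikely.
- **Possibly** asks for reasonable timing and an event "that follows a known or expected response pattern to that suspected drug", and adds a condition on other causes: "but that could readily have been produced by a number of other factors".
- **Unrelated** is "An event that can be determined with certainty to have no relationship to the study drug".

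There is no unlikely, not-assessable or residual class.

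The same section lists what goes into the study database for each event, including "its relationship to the drug(s) of interest (suspected/not suspected". No criteria are given for those two levels, and nothing links them to the four in Table 2. Section 9.1.06 sends the relation to study drug to the case report form, again without naming a scale.

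Safety is the fourth secondary endpoint (section 5.2). Section 14.2, like the synopsis, plans this: "All reported adverse events will be summarized by the number of subjects reporting adverse events, body system, severity, seriousness, and relationship to study treatment".

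On serious events, section 11.2 requires reporting whatever the cause until four weeks after participation stops. Later events "should only be reported if considered by the Investigator attributable to the exposure to the investigational drug(s) during the trial period".

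**The concern.** A causality scale should have a place for every event an investigator may meet. This one makes prior knowledge of the reaction a condition for calling it related, and makes certainty a condition for calling it unrelated. The event caught between the two is the one a safety review most wants to see: a reaction not previously attributed to the drug.

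An investigator who meets such an event must force it into a class whose definition it fails, or leave the field blank. Different assessors, or the same assessor on different days, may choose differently. With two relatedness records in one section and neither named in the analysis text, the planned summary by relationship could be built in more than one way and give different answers.

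**Working it through.** The documents give no figure on this point, so the check is to take Table 2 literally and see which events it can hold.

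**Inputs, all from Table 2**

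- K: already known toxicity (yes/no)
- T: reasonable temporal sequence (yes/no)
- P: known or expected response pattern (yes/no)
- D: confirmed by stopping or reducing the drug (yes/no)
- A: alternative explanation (none, unlikely, ready)

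Only events that cannot be ruled out with certainty are considered, because the others go to Unrelated.

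**Rules**

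- Definitely: K, or (T and P and D and A = none)
- Probably: T and P and D and A = none or unlikely
- Possibly: T and P and A = ready

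This lets a known toxicity qualify on its own, which is the generous reading. If the later conditions applied to it as well, the number of unclassed combinations could only rise.

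**Count**

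All combinations: 2 × 2 × 2 × 2 × 3 = 48. Those with a known toxicity but no known pattern are impossible: 2 × 2 × 3 = 12. That leaves 48 − 12 = 36.

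| Group | Combinations | Fit no class |
|---|---|---|
| No known pattern | 12 | 12 |
| Known pattern, not an established toxicity | 12 | 8 |
| Established toxicity | 12 | 0 |
| Total | 36 | 20 |

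In the first row every combination falls out, including good timing, positive dechallenge and no other explanation.

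In the second row, 6 fall out because timing is not reasonable. Another 2 have good timing but no dechallenge, with alternative causes absent or unlikely: Definitely and Probably need the dechallenge, and Possibly needs a ready alternative cause. The other 4 are classed (6 + 2 + 4 = 12). Those 2 are not remote cases. Section 8.3 sets one fixed regimen until week 50 and no dose reduction is described, so subjects who stay on schedule will often provide no dechallenge information.

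The counts are combinations of criteria, not forecasts of event frequency.

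**Size in the table**

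At full enrolment of 30, each affected subject moves a relatedness proportion by 1/30 = 3.3 percentage points. The documents give nothing from which to estimate how many subjects would be affected.

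**The case against.** The strongest reply is that the gap may never reach a reported result. The item that section 11.1 says goes into the database has two levels and can hold every event, and section 14.2 does not say that Table 2 is tabulated. A reader might infer that the relatedness summary is bound to be wrong. The documents do not support that, since the two-level item may be the one used and nothing says it is derived from Table 2. What stands is that the two-level item has no criteria, that Table 2 is the only definition of relatedness given, and that the choice between them is open.

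A reader might also infer that any unlikely event is left without a class. That goes too far. An event with reasonable timing, a known pattern and ready alternative causes fits Possibly. The doubtful events that fall out are those lacking the timing or the pattern that are neither an established toxicity nor excludable with certainty.

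Nor are novel reactions lost. All adverse events are recorded, and section 14.2 also summarises them by number of subjects, body system, severity and seriousness. No hypothesis test, threshold or stopping rule in the documents rests on the relatedness count. This reply stands, and it limits the severity.

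Finally, a reader might infer that serious events will go unreported. Up to four weeks after participation ends, section 11.2 makes reporting independent of causality. (Section 11.3 ends collection at the final visit; that is a separate discrepancy, but it too covers events whether or not related.) After four weeks the test is the investigator's view of attribution, with no reference to Table 2. Late reporting could be affected only if Table 2 is used to form that view.

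**Conclusion.** The point holds as a minor defect. Table 2 is a written rule that is not exhaustive: 20 of 36 possible combinations of its own criteria have no class, including every unexpected reaction that cannot be ruled out with certainty. The two relatedness scales are not reconciled, and the planned summary does not say which it uses. A summary on the Table 2 scale may therefore be inconsistent or misclassify novel reactions, at 3.3 percentage points per affected subject if 30 are enrolled.

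This rests on a literal reading of the table and on the possibility, neither stated nor excluded, that Table 2 feeds the summary or late attribution. The primary endpoint is not affected, nor is serious-event reporting up to four weeks after participation ends.

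**What to change.** 1. In Table 2, make the known or expected pattern supporting rather than mandatory evidence in the related classes. Redefine Possibly so that a reasonable temporal sequence is enough, whether or not other factors could have produced the event. Both its pattern condition and its alternative-cause clause must go. If only the pattern condition were dropped, a novel reaction with no other explanation would still fail the definition.
2. For Unrelated, replace certainty by the absence of a reasonable possibility of a relationship, or add an Unlikely class.
3. In section 14.2, name the scale to be tabulated and state the mapping: Definitely, Probably and Possibly count as suspected; Unlikely and Unrelated count as not suspected.

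Since the reworded classes overlap, add one line on order: an event with no reasonable possibility of a relationship goes to Unrelated even if its timing fits, and any other event takes the strongest class it meets.

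As a check, of the 20 unclassed combinations, 8 have reasonable timing (6 without and 2 with a known pattern) and would become at least Possibly, unless judged to have no reasonable possibility of a relationship. The other 12 lack it and would go to Unlikely, or to the reworded Unrelated if the investigator sees no reasonable possibility.

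The cost is the wording of one table, one code list on the case report form and a sentence in section 14.2. A few more events will be classed as possibly related. The analysis plan promised in section 14 could settle item 3, but items 1 and 2 belong in the protocol because events are classified when they are recorded.

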11.2 Serious Adverse Experiences (SAE)

A SAE is any untoward medical occurrence that at any dose:

- results in death,
- is life-threatening,
- requires inpatient hospitalization or prolongation of existing hospitalization,
- results in persistent or significant disability/incapacity,
- is a congenital anomaly/birth defect,
- is otherwise a significant medical event.

This includes any SAEs likely to arise from the trial indication or progression of underlying/concomitant illness(es) (e.g. progression of cancer in oncology trials), unless specified in the protocol as study specific exemptions.

Any SAE, irrespective of causality, occurring after the subject has provided informed consent and until four weeks after the subject has stopped study participation must be reported unless otherwise stated in the protocol. SAEs occurring after four weeks from ending study participation should only be reported if considered by the Investigator attributable to the exposure to the investigational drug(s) during the trial period. This includes the period in which the study protocol interferes with the standard medical treatment given to a subject, even if study treatment has not yet started (e.g. withdrawal of previous treatment during washout period, change in treatment to a fixed dose of concomitant medication).

11.3. Serious Adverse Experience Reporting

Study sites will document all SAEs that occur (whether or not related to study drug) per [UCSF CHR Guidelines](#). The collection period for all SAEs will begin after informed consent is obtained and end after procedures for the final study visit have been completed.

SAEs occurring after four weeks from ending study participation should only be reported if considered by the Investigator attributable to the exposure to the investigational drug(s) during the trial period. This includes the period in which the study protocol interferes with the standard medical treatment given to a subject, even if study treatment has not yet started (e.g. withdrawal of previous treatment during washout period, change in treatment to a fixed dose of concomitant medication).

In accordance with the standard operating procedures and policies of the local Institutional Review Board (IRB)/Independent Ethics Committee (IEC), the site investigator will report SAEs to the IRB/IEC.

Timelines: All serious adverse events (SAEs) must be reported by the sites to Sponsor within 24 hours of occurrence of the SAE. The timelines for investigator initiated trials reporting to Regeneron Pharmaceuticals will be done as per Third Party Study/Investigator Initiated Trial Agreement. All reports must be sent to Regeneron as below:

- Fax SAE/CIOMS or MedWatch Reports to [contact]
- Email forms to [contact]

Follow-up reports: SAEs will be followed until resolution or until it is judged to be permanent, and an assessment will be made at each visit (or more frequently, if necessary) of any changes in severity, the suspected relationship to the drug of interest, the interventions required to treat it, and the outcome.

The Sponsor shall support Regeneron in the following-up of all SAEs so that complete information is available to maintain patient safety and also as part of any commitments by Regeneron to any Health authority OR specific Health authority follow-up requests for the product under investigation.

Pregnancies: Any occurrences of a pregnancy in a patient (or a patients partner) during study participation will be collected. All pregnancies will be followed up to determine outcome, including spontaneous or voluntary termination, details of the birth, and the presence or absence of any birth defects, congenital abnormalities, or maternal and/or newborn complications.

12 DISCONTINUATION AND REPLACEMENT OF SUBJECTS

12.1 Early Discontinuation of Study Drug

A subject may be discontinued from study treatment at any time if the subject, the investigator, or the Sponsor feels that it is not in the subject's best interest to continue. The following is a list of possible reasons for study treatment discontinuation:

- Subject withdrawal of consent (or assent)
- Subject is not compliant with study procedures
- Adverse event that in the opinion of the investigator would be in the best interest of the subject to discontinue study treatment
- Protocol violation requiring discontinuation of study treatment
- Lost to follow-up
- Sponsor request for early termination of study
- Positive pregnancy test (females)

If a subject is withdrawn from treatment due to an adverse event, the subject will be followed and treated by the Investigator until the abnormal parameter or symptom has resolved or stabilized.

All subjects who discontinue study treatment should come in for an early discontinuation visit as

soon as possible and then should be encouraged to complete all remaining scheduled visits and procedures.

All subjects are free to withdraw from participation at any time, for any reason, specified or unspecified, and without prejudice.

Reasonable attempts will be made by the investigator to provide a reason for subject withdrawals. The reason for the subject's withdrawal from the study will be specified in the subject's source documents. Refer to Section 10.13 for early termination procedures.

12.2 Withdrawal of Subjects from the Study

A subject may be withdrawn from the study at any time if the subject, the investigator, or the Sponsor feels that it is not in the subject's best interest to continue.

All subjects are free to withdraw from participation at any time, for any reason, specified or unspecified, and without prejudice.

Reasonable attempts will be made by the investigator to provide a reason for subject withdrawals. The reason for the subject's withdrawal from the study will be specified in the subject's source documents. As noted above, subjects who discontinue study treatment early (i.e., they withdraw prior to Visit 11) should have an early discontinuation visit. Refer to Section 10.13 for early termination procedures. Subjects who withdraw after Visit 1 but prior to Visit 10 should be encouraged to come in for a final visit (and the procedures to be followed would include those for their next scheduled visit). Subjects who sign the informed consent form (ICF) and who are discontinued or withdraw from the study before study product administration will be defined as screen failures. No data will be collected in the CRFs for screen failure subjects.

13 PROTOCOL VIOLATIONS

A protocol violation occurs when the subject, investigator, or Sponsor fails to adhere to significant protocol requirements affecting the inclusion, exclusion, subject safety and primary endpoint criteria. Protocol violations for this study include, but are not limited to, the following:

- Failure to meet inclusion/exclusion criteria.
- Use of a prohibited concomitant medication.
- Non-compliance with study drug regimen.
- Non-compliance with study visit procedures.
- Failure to comply with Good Clinical Practice (GCP) guidelines will also result in a protocol violation. The PI will determine if a protocol violation will result in withdrawal of a subject.

When a protocol violation occurs, it will be discussed with the investigator and a Protocol Violation Form detailing the violation will be generated. This form will be signed by a Sponsor representative and the Investigator. A copy of the form will be filed in the site's regulatory

binder and in the Sponsor's files.

14 STATISTICAL METHODS AND CONSIDERATIONS

Prior to the analysis of the final study data, a detailed Statistical Analysis Plan (SAP) will be written describing all analyses that will be performed. The SAP will contain any modifications to the analysis plan described below.

14.1 Analysis of Primary Endpoint

The primary endpoint is improvement of PGWB at week 16 compared to baseline. Statistical significance will be based on resulting p-values of 0.05 or less. Last observation carried forward (LOCF) will be used to impute missing data. Analyses will be conducted on an intent-to-treat (ITT) population (all subjects enrolled and receiving the treatments). Analyses on the per-protocol (PP) population will be considered supportive of the ITT analyses. Subjects will be eligible for the PP analyses if they complete the 52 week evaluation without any noteworthy study protocol violations (i.e. failure to use the study medications or investigator activity that could have possibly interfered with the therapeutic administration of the treatment or the precise evaluation of treatment efficacy).

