5.2 Secondary Analysis Endpoints

1. Improvement in work productivity measured by change in Work Productivity and Activity Impairment scale (WPAI) at Week 16 from baseline
2. Improvement in quality of life measured by change in Dermatology Life Quality Index (DLQI) at Week 16 from baseline
3. Efficacy of drug as measured by EASI and IGA at week 16 from baseline
4. Safety of drug
5. Improvement in itch and pain scores using numerical rating scales at Week 16 from baseline
6. Improvement in sleep quality measured by the Pittsburgh Sleep Quality Assessment (PSQI) at Week 16 from baseline
7. Evaluation of subjective video documentation

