8.3 Dosage/Dosage Regimen

Dupilumab will be administered at an initial dose of 600 mg subcutaneously followed by 300 mg subcutaneously through the study, which is the FDA-approved and recommended dose for dupilumab. There is no weight-based dosing. The dosing schedule will be as follows: dupilumab 600mg subcutaneously once at week 0, followed by dupilumab 300 mg subcutaneously every other week until week 50.

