8.4 Administration Instructions

Doses of study treatment will be administered at the study site after the study assessments for the visit have been completed, at visits occurring between weeks 0 and 48. Subjects will administer the medication independently every other week only after they have demonstrated the competency to self-administer the treatment outside of the study site. Patients not demonstrating competency to self-administer the treatment will be administered the medication at the study site as needed. There will be no study medication given after week 50 of the study.

The subject should be instructed to contact the investigator if he/she is unable for any reason to attend a study visit as scheduled. All dates and times of injections done to the subject during the study must be recorded on the Dosage Administration Record CRF. The investigator will promote compliance by instructing the subject to attend the study visits as scheduled and by stating that compliance is necessary for the subject's safety and the validity of the study.

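### The per-protocol set for a Week 16 endpoint requires completion of Week 52, so later events remove patients whose Week 16 data are complete and compliant

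*Combined protocol and SAP*

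**What the plan says.** Section 14.1 fixes the time point: "The primary endpoint is improvement of PGWB at week 16 compared to baseline". The same paragraph gives the PP rule: "Subjects will be eligible for the PP analyses if they complete the 52 week evaluation without any noteworthy study protocol violations". The examples of a noteworthy violation include "failure to use the study medications or investigator activity that could have possibly interfered with the therapeutic administration of the treatment", with no date limit. The statistics entry of the synopsis carries the same endpoint and rule. The PP analysis has a secondary role: "Analyses on the per-protocol (PP) population will be considered supportive of the ITT analyses".

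Every secondary endpoint in section 5.2 that has a time point is also at Week 16, for example "Efficacy of drug as measured by EASI and IGA at week 16 from baseline". No endpoint in section 5 is set at Week 52, although the objectives in sections 3.1 and 3.2 refer to 52 weeks of treatment.

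Three other provisions bear on the point. Section 8.3 has an initial dose at Week 0, "followed by dupilumab 300 mg subcutaneously every other week until week 50". Section 8.4 fixes the order within a visit: "Doses of study treatment will be administered at the study site after the study assessments for the visit have been completed". Section 12.1 says that patients who stop study drug "should be encouraged to complete all remaining scheduled visits and procedures".

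**The concern.** A PP analysis of a Week 16 endpoint should show the result in patients treated and assessed as planned up to Week 16. Here membership also depends on the following 36 weeks. A patient can be fully compliant through Week 16, have a valid PGWB at that visit, and still be excluded for leaving at Week 20. A patient who stops drug at Week 40 but attends every remaining visit, as section 12.1 encourages, completes Week 52 yet can be excluded for not using the medication. Neither event can have altered a value already recorded.

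Two things are at stake. The PP set loses valid data from a study of at most 30 patients. And if staying in the study after Week 16 depends on how well the patient was doing at Week 16, the PP mean is that of a selected group. A difference between the PP and ITT results could then reflect later retention and not adherence during the period that the endpoint covers.

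**Working it through.** The plan states no figure to reproduce: section 14.3 bases the sample size on the size of earlier studies, without effect size, SD, power or dropout. The check has three steps.

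**1. How much of the exclusion window lies after the endpoint (documents only)**

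- Dosing occasions (section 8.3): Weeks 0, 2, …, 50, so 50/2 + 1 = 26.
- Before the Week 16 assessment: Weeks 0 to 14, so 14/2 + 1 = 8. The Week 16 dose counts as after, because on-site dosing follows assessment (section 8.4).
- After it: 26 − 8 = 18, and 18/26 = 69%.
- PGWB visits (section 9.1.08): Weeks 0, 4, …, 52, so 14, of which 9 (Weeks 20 to 52) come after Week 16.
- Time after the endpoint: 52 − 16 = 36 weeks.

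These counts show opportunity for late exclusion. They do not estimate how many patients would be excluded.

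**2. Effect on precision and on the mean (assumed loss)**

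Assume 30 patients with Week 16 data, of whom a share p is later lost from the PP set. Let X be the standardised Week 16 change, X ~ N(0,1), higher being better. Model later loss as logit P(loss) = a − ln(OR)·X, with a solved so that the overall loss is p, and OR the odds ratio of loss per SD worse response. The mean and SD of X among the patients kept follow by numerical integration. The half-width is t(0.975, n−1) × SD/√n. For reference, n = 30 with SD 1 gives 0.373.

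Each cell gives mean shift / SD of patients kept / half-width, in SD units:

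| p | n | OR 1 | OR 1.5 | OR 2 | OR 3 |
|---|---|---|---|---|---|
| 10% | 27 | 0 / 1.000 / 0.396 | 0.040 / 0.993 / 0.393 | 0.066 / 0.981 / 0.388 | 0.098 / 0.959 / 0.379 |
| 20% | 24 | 0 / 1.000 / 0.422 | 0.079 / 0.988 / 0.417 | 0.129 / 0.968 / 0.409 | 0.186 / 0.934 / 0.395 |
| 30% | 21 | 0 / 1.000 / 0.455 | 0.118 / 0.984 / 0.448 | 0.190 / 0.959 / 0.436 | 0.270 / 0.917 / 0.418 |

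If better responders leave more often (OR 1/1.5, 1/2, 1/3), the shifts have the same size and a negative sign.

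**3. Cross-check with a different model**

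Assume a total 52-week dropout D at constant hazard among 30 patients. Then n(16) = 30(1−D)^(16/52), n(52) = 30(1−D), and the share of Week 16 patients lost later is q = 1 − n(52)/n(16). If retention correlates ρ with the Week 16 change, the shift in SD units is ρ·φ(z_q)/(1−q), where φ is the standard normal density and z_q its q-quantile.

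| D | n(16) | n(52) | Lost after Week 16 | Shift, ρ = 0.3 | Shift, ρ = 0.5 |
|---|---|---|---|---|---|
| 5% | 29.5 | 28.5 | 1.0 | 0.024 | 0.040 |
| 10% | 29.0 | 27.0 | 2.0 | 0.043 | 0.072 |
| 20% | 28.0 | 24.0 | 4.0 | 0.079 | 0.132 |
| 30% | 26.9 | 21.0 | 5.9 | 0.113 | 0.189 |
| 40% | 25.6 | 18.0 | 7.6 | 0.148 | 0.247 |

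With ρ = 0 the shift is zero. At D = 20% the standard error rises by a factor √(28.0/24.0) = 1.08. The two models give shifts of similar size.

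**The case against.** The strongest reply is that little depends on this. The PP analysis is supportive, no decision rule uses it, and the ITT set of all enrolled and treated subjects loses nobody. That stands, and it limits the importance of the point. A supportive analysis must still address the endpoint it supports.

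The size of the harm is assumed throughout. The documents give no dropout rate and no link between response and retention; zero and negative shifts are possible, and even the largest shift shown, 0.27 SD, lies within its half-width of 0.42 SD. This also stands: the figures are illustrations. If nobody leaves or commits a noteworthy violation after Week 16, nobody is dropped.

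The term noteworthy has no threshold, and part of its explanation concerns interference with the evaluation of efficacy. A late missed dose might therefore be judged irrelevant to Week 16. That weakens the argument from dose counts, but completing Week 52 is a separate and unconditional requirement.

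The objectives are framed over 52 weeks, which may explain the rule. Yet no Week 52 endpoint is defined, and the rule is stated in the same paragraph as the Week 16 endpoint. It is fair to add that section 14.2 does not mention a PP set, so its use for the secondary endpoints is inferred; the mismatch holds on the primary endpoint alone. Section 14 promises a detailed SAP that may modify the plan, but the documents contain no revised definition.

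**Conclusion.** The concern holds. As written, the PP rule excludes patients with complete, compliant Week 16 data because of events up to 36 weeks later that cannot have affected the endpoint. This follows from the text and needs no assumption.

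Its numerical effect does rest on assumptions. With 10 to 30% of 30 patients lost after Week 16, the PP set has 27 to 21 patients. If loss is unrelated to response there is no bias, and the half-width rises from 0.37 SD to between 0.40 and 0.46 SD. If loss is related to response with an odds ratio of 1.5 to 3 per SD, the PP mean moves by 0.04 to 0.27 SD: upward if poorer responders leave, which seems the likelier case but is not documented, and downward if better responders leave. The primary ITT result is untouched. The rule should be corrected, but it does not threaten the main analysis.

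**What to change.** In the synopsis, in section 14.1 and in the SAP, define the PP set for Week 16 endpoints as ITT subjects who have a Week 16 evaluation and no noteworthy protocol violation up to and including that evaluation. Keep the 52-week completion rule only for a separately named set, to be used if Week 52 analyses are specified. The new cut-off does not settle what counts as noteworthy, so the SAP should also list the qualifying violations.

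The cost is one sentence in the synopsis and one in section 14.1, carried into the SAP that section 14 says is still to be written. No new data, visits or patients are needed. Under the constant-hazard illustration, tying completion to Week 16 would retain about 1.0, 2.0, 4.0, 5.9 or 7.6 more patients at 5, 10, 20, 30 or 40% total dropout, before counting those otherwise excluded for late violations.
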